##### 9.1.1.1 **Solicited Adverse Events**

Solicited **systemic** AEs (fever, headache, fatigue, chills, myalgia, arthralgia, nausea/vomiting, and diarrhea) will be recorded from Day -7 until Day -1 using a paper diary. These records shall provide a baseline for reactogenicity and safety for each enrolled subject.

Solicited **local** AEs (injection site pain, redness, swelling, and itching) and solicited **systemic** AEs will be recorded on the days of vaccination (Day 1 and Day 29) and the following 7 days using a paper diary.

Body temperature should be measured orally and by using the thermometer provided to the subject at Visit 1.

Solicited AEs will be assessed on an intensity scale of absent, mild, moderate, and severe (Table 2 and Table 3). In case of related Grade 3 solicited or unsolicited AEs reported for more than 1 day in the diary, the subject will be questioned to establish the total duration of the AE as exactly as possible and this information will be recorded in the eCRF.

Solicited systemic Grade 3 AEs and unsolicited Grade 3 AEs, except for solicited injection site reactions, must be reported to the medical monitor without delay, on the same day of awareness by the site.

By definition, all solicited local AEs occurring from the time of first vaccination are considered related to trial vaccination. For solicited systemic AEs, the Investigator will assess the relationship between trial vaccine and each occurrence of each AE.

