#### **9.1.1.2 Unsolicited Adverse Events and Serious Adverse Events**

Diaries will also be used for collection of unsolicited AEs in the week before the first vaccination as well as on each vaccination day and the following 28 days. In addition, subjects will be contacted by phone to verify whether they had any health concerns since the last visit.

The occurrence of AEs (serious and non-serious) will be assessed by non-directive questioning of the subject at each visit. AEs volunteered by the subject during or between visits in the diary or detected through observation, physical examination, laboratory tests, or other assessments during the entire trial, will be recorded in the eCRF, if they fall within the reporting period. Subjects should be instructed to report immediately any AEs with serious symptoms, subjective complaints or objective changes in their well-being to the Investigator or the site personnel, regardless of the perceived relationship between the event and the trial vaccine.

The Investigator will assess the relationship between trial vaccine and each occurrence of AE/SAE.

SAEs and AEs leading to vaccine withdrawal or trial discontinuation will be collected throughout the trial.

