#### For resolution date:

- If date of resolution is completely missing, it is assumed that it resolved at the date of the end of the AE assessment period.
- If year is present, it is assumed that it resolved on 31 December of that year (i.e., 31DECYYYY), or at the end of the AE assessment period if earlier.
- If year and month are present, it is assumed that it resolved on the last day of that month, or at the end of the AE assessment period if earlier.

No other safety variables will be imputed. In case the number of missing/partial dates for solicited local AEs, solicited systemic AEs or individual solicited AEs is higher than expected for the analysis of durations (in days), a sensitivity analysis will be conducted to assess the impact on the primary endpoint.

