8.5 End of the Trial Definition

A subject is considered to have completed the trial when he/she has completed all visits.

End of Trial is defined as the point at which the last subject has completed the last visit.

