9.4 Estimands

Based on the Protocol Amendment #1, a subset of endpoints will be presented. See Section 6.1, 6.2, 6.3 and 6.4 and Appendix 4 List of Abbreviated Scope Based on SAP Version 2.0 for additional details.

ENDPOINTS (subject level)	ESTIMANDS (population level)
Primary Safety	

The frequency, intensity, and duration of solicited local AEs on each vaccination day and the following 7 days.
 
The frequency, intensity, duration, and relationship to trial vaccination of solicited systemic AEs on each vaccination day and the following 7 days.
 
The occurrence, intensity and relationship to trial vaccination of unsolicited AEs on each vaccination day and the following 28 days.
 
The occurrence and relationship to trial vaccination of SAEs and AESIs throughout the trial.
	
In subjects who received at least one dose of CVnCoV vaccine and a post baseline vaccine safety assessment is available. Subjects receiving an authorized/licensed COVID-19 vaccine during the course of the trial will be censored at the day after intake. The primary safety will be analyzed with the safety analysis set.
 
The number and percentage of subjects overall and by co-morbidity:
 
Each solicited local AE within 7 days (after each trial vaccination by intensity and overall).
 
Each solicited systemic AE within 7 days after each trial vaccination by intensity, by relationship to trial vaccine and overall.
 
The mean duration in days by group with standard deviation of solicited AEs (within the solicited period, total duration).
 
At least 1 unsolicited AEs, at least 1 grade unsolicited AEs and each unsolicited AEs by SOC/PT occurring within 28 days after each trial vaccination and overall by causal relationship to trial vaccine and overall.
 
At least 1 SAE, or at least 1 AESI to vaccine overall by causal relationship to trial vaccine and overall.

ENDPOINTS (subject level)	ESTIMANDS (population level)
Primary Immunogenicity	

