 - If date of resolution is completely missing, and it is assumed that it resolved at the date of the end of the trial, the date of the end of the trial is used as the AE end date.
 - If year is present, it is assumed that it resolved on 31 December of that year (i.e., 31DECYYYY), or at the end of the trial if this is earlier and in the same year.

- If year and month are present, it is assumed that it resolved on the last day of that month, or at the end of the trial if this is earlier and in the same month/year.
- Imputation of missing AE start times:
 - If the (recorded or imputed) AE start date is equal to the vaccination start date, then the AE start time will be the time of vaccination start.
 - In all other cases, AE start time will be imputed as 00:00.

If not stated otherwise, the original or incomplete data will be presented in listings rather than the imputed one.

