10.7.2.1.1 Duration of Solicited Adverse Events

Duration of solicited local and systemic adverse events are defined as the sum consecutive days with local/systemic adverse events (days 1 to 8) for the same grade. For example, Fatigue with grade 1 occurring on day 2 and 3 and day 7 will be counted as two separate events with the duration 2 days and 1 day. For the duration of solicited local and systemic AEs ongoing beyond Day 8 the following definition is used:

If the AE is present on day 8 in the diary and the same AE is present on day 9 on the eCRF, the sum of days between the date of day 9 and end date for the AE on the eCRF is added to the consecutive days as collected on the diary. If the duration of any AE continues after the next dose and the subject experience an AE of the same type in the second dose, these two events will be presented separately.

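### SAP 10.5 closes adverse events with missing end dates at the end of the trial instead of the protocol's AE assessment period, an undeclared change that can inflate the total-duration summary of solicited reactions

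*SAP*

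**What the plan says.** SAP 10.5 has three rules for AE end dates. When the date is completely missing and the event is taken to have resolved when the trial ended, "the date of the end of the trial is used as the AE end date"; no rule covers the case where that assumption is not made. Partial dates go to the end of the recorded year or month, or to the end of the trial if that is earlier.

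Protocol 10.3.6 has the same three steps with a different stopping point. For a completely missing date "it is assumed that it resolved at the date of the end of the AE assessment period"; partial dates go to year end or month end, "or at the end of the AE assessment period if earlier". That period is not defined. Protocol 9.1.1.1 says that solicited reactions "will be recorded on the days of vaccination (Day 1 and Day 29) and the following 7 days using a paper diary". Protocol 9.1.1.2 has unsolicited events collected by diary in the week before the first vaccination "as well as on each vaccination day and the following 28 days".

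The other relevant SAP text:

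- 8.5: "End of Trial is defined as the point at which the last subject has completed the last visit".
- 10.7.2.1.1: duration is a run of consecutive diary days at one grade. For a reaction present on diary Day 8 and on the eCRF at Day 9, "the sum of days between the date of day 9 and end date for the AE on the eCRF is added", with no upper limit.
- 9.4, primary safety: "The mean duration in days by group with standard deviation of solicited AEs", in two versions, one within the solicited period and one for total duration.
- Appendix 4: the duration table (14.3.2.6.1) stays in the abbreviated scope.

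SAP 2.0, 6.3 and 6.4, where changes are recorded, do not mention the new stopping point. The protocol also promises a sensitivity analysis if missing or partial dates for solicited events are more frequent than expected. The SAP contains none.

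**The concern.** The two documents give different answers for the same missing value, and the SAP's answer feeds a primary safety endpoint. Because 10.7.2.1.1 sets no cap, an imputed eCRF end date passes straight into total duration, which the estimand summarises by a mean and SD. A mean of mostly short reactions is easily moved by a few values of three months or more. Only 129 subjects were enrolled, results are shown by seven co-morbidities, and no control arm would expose the artefact.

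The SAP rule also sits badly with its own text. If the end of the trial is the last subject's last visit (8.5), the imputed date can fall after a subject's own last contact. It can also fall after the day from which 10.9 censors safety data, namely the day after an authorised or licensed vaccine. The reaction would then be credited with days nobody observed, or with days the SAP says to leave out.

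**Working it through.** **The plan's own figures.** SAP 10.7.2.1.1 gives an example: fatigue at one grade on days 2, 3 and 7. Counting consecutive runs gives events of 2 days and 1 day, as stated. The amended schedule's Day 120 also agrees: 29 + 91 = 120.

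**Imputed duration of one event with no end date.** Take a reaction present at one grade on all 8 diary days, on the eCRF at Day 9, and closed at the subject's own end-of-trial visit (Day 120 after two doses, Day 91 after one). Duration = 8 + days from diary Day 9 to closure, inclusive.

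| Event | Diary Day 9 is | Closed at | SAP duration |
|---|---|---|---|
| After dose 2 | Day 37 | Day 120 | 8 + 84 = 92 days |
| After dose 1, two-dose subject | Day 9 | Day 120 | 8 + 112 = 120 days |
| After dose 1, one-dose subject | Day 9 | Day 91 | 8 + 83 = 91 days |

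Each is one day shorter if Day 9 is not counted, and longer if the trial-level date of SAP 8.5 is used. Under the protocol the event lasts 8 days if the assessment period is the diary window (vaccination day + 7), or 29 days if it is vaccination day + 28. For a dose-2 event the gap is 92 − 8 = 84 days or 92 − 29 = 63 days. A later onset shortens both sides equally.

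**Effect on the mean.** With N events, k of them unresolved with imputed length L, and the others averaging m days:

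mean = [(N − k)·m + k·L] / N

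The documents do not give m, k or N. I assume m = 2 days and dose-2 events. N = 129 takes one event per enrolled subject. N = 18 is an even split over seven co-morbidities (129/7 = 18.4). N = 400 stands for a large pooled row.

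| k of N | SAP (L = 92) | Protocol, L = 8 | Protocol, L = 29 |
|---|---|---|---|
| 5 of 129 | (248 + 460)/129 = 5.49 | (248 + 40)/129 = 2.23 | (248 + 145)/129 = 3.05 |
| 1 of 18 | (34 + 92)/18 = 7.00 | (34 + 8)/18 = 2.33 | (34 + 29)/18 = 3.50 |
| 3 of 400 | (794 + 276)/400 = 2.67 | (794 + 24)/400 = 2.04 | (794 + 87)/400 = 2.20 |

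The ratios of SAP to protocol mean are 2.5 and 1.8 in the first row, 3.0 and 2.0 in the second, and 1.3 and 1.2 in the third.

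**Share of unresolved events that doubles the mean.** Setting the SAP mean to twice the protocol mean gives f = m / (L_SAP − 2·L_protocol + m). With m = 2 this is 2/(92 − 16 + 2) = 2.6% against 8 days, or 2/(92 − 58 + 2) = 5.6% against 29 days. Over m = 1.5 to 4 days the ranges are 1.9% to 5.0% and 4.2% to 10.5%.

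**The case against.** The case for leaving the plan alone has real weight.

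- **Few events are exposed.** A reader might infer that any solicited reaction lacking an end date becomes a reaction of months. The documents do not support that. A reaction gone by diary Day 8 gets its duration from the diary and needs no end date.
- **A bounded summary is reported alongside.** The version within the solicited period cannot exceed 8 days. This stands.
- **The protocol's stopping point is unclear.** A reader might take it as settled that solicited events close on vaccination day + 7. The term is undefined. A 28-day reading is possible, and the observation period in Protocol Appendix 9 runs to the end of the trial for the period described in Section 9.1.1.
- **Restoring the protocol rule is not a clean repair.** Closing on Day 8 contradicts an eCRF that shows the event on Day 9. With closure no earlier than Day 9 the event lasts at least 9 days, and 5 of 129 gives (248 + 45)/129 = 2.27, so the comparison hardly changes.
- **Skewness would show.** SAP 12.0 makes the median, quartiles and maximum default statistics, and listings show unimputed dates by default. This softens the harm, but the estimand still names the mean, and no planned output counts the imputed values.
- **Missing end dates may be rare.** Protocol Appendix 9 requires follow-up until the outcome is known or no more can be learned, and Protocol 11.4 requires queries. That such dates are common in chronic disease is plausible, but no figure supports it.
- **The sensitivity analysis may survive.** The SAP is to be read with the protocol, and the analysis is conditional. Even so, nobody is told to program it.

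None of this explains the undeclared difference or removes the missing upper bound.

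**Conclusion.** The point holds within limits. SAP 10.5 departs from Protocol 10.3.6 without saying so, and the departure reaches the mean and SD of total duration for solicited reactions still present at Days 8 and 9 with no end date. Under the stated assumptions a handful of such events can roughly double the mean for a single symptom or for 129 events, and one can double or triple it in a cell of 18. A large pooled row moves little. The sizes are scenarios, because event counts, the missing-date rate and the average duration of resolved events are all assumed.

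It would go too far to say that the primary safety results as a whole are distorted. Incidence and grade are untouched, the bounded duration summary is untouched, and for SAEs and AESIs, collected throughout the trial, the two rules coincide. The analyses are descriptive. The point should be fixed before database lock, but it is not fatal to the plan.

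**What to change.** - **Reconcile and define.** Align SAP 10.5 with Protocol 10.3.6, define both the AE assessment period and the end of the trial, and state a rule for a completely missing date when resolution at the end of the trial is not assumed. If the change is intended, declare it in SAP 6.4 with the reason.
- **Bound the imputed date.** It should never be later than the subject's own last contact or the SAP 10.9 censoring date, and never earlier than the last day on which the event is recorded as present.
- **Report the imputation.** In Table 14.3.2.6.1, show the number of events with an imputed end date or still ongoing.
- **Reinstate the sensitivity analysis.** Repeat total duration under the protocol rule and again without imputed end dates.

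The cost is SAP wording, a small programming change, one added count and the repeated runs of total duration. The drawback is that durations of genuinely unresolved events are truncated, which the count discloses.

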10.6 Prior/Concomitant Medication

Prior medications are medications with a start date prior first dose date of vaccination. Concomitant medications are those ongoing at or starting on or after first dose date of vaccination.

10.7 Adverse Events (AEs)

Since no control group is included in the trial, the subjects will serve as their own control for reactogenicity and safety assessments. For this purpose, the subjects will complete the pre-vaccination diary card on a daily basis as of Day -7 (i.e., during 1 week before the first vaccination) to give an indication of their normal life with co-morbidities. Solicited systemic AEs as well as unsolicited AEs will need to be collected similar to what is done during the 7 days after vaccination.

10.7.1 Treatment Emergent Adverse Events (TEAEs)

A TEAE is any AE that first occurs or increases in severity or relationship to trial vaccine after the first dose of vaccine. AEs which change in severity or relationship to trial vaccine are assigned a new start date and captured as a new record in the CRF. Hence, an AE is defined as TEAEs if the start date/time is after the date/time of first vaccination. Imputed AE start date/time as defined in Section 10.5 will be considered when assessing if an AE is treatment emergent. If the AE start date is still missing after applying imputation rules (i.e. missing year), the AE will be considered treatment emergent.

All Solicited AEs are considered treatment emergent, even in the case that (partially) missing or conflicting date/time information is recorded or imputed.

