

• The Investigator is obligated to perform or arrange for the conduct of supplemental measurements and/or evaluations as medically indicated or as requested by the CRO to elucidate the nature and/or causality of the AE or SAE as fully as possible. This may include additional laboratory tests or investigations, histopathological examinations, or consultation with other health care professionals.

• If a subject dies during participation in the trial or during the follow-up period, the Investigator will provide the CRO with a copy of any post-mortem findings including histopathology.

• New or updated information will be recorded in the originally completed eCRF.

• The Investigator will submit any updated SAE data to the CRO within 24 hours of receipt of the information.

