10.7.3 Unsolicited Adverse Events and Serious Adverse Events

Diaries will also be used for collection of unsolicited AEs in the week before the first vaccination as well as on each vaccination day and the following 28 days. In addition, subjects will be contacted by phone to verify whether they had any health concerns since the last visit.

The occurrence of AEs (serious and non-serious) will be assessed by non-directive questioning of the subject at each visit. AEs volunteered by the subject during or between visits in the diary or detected through observation, physical examination, laboratory tests, or other assessments during the entire trial, will be recorded in the eCRF, if they fall within the reporting period. Subjects should be instructed to report immediately any AEs with serious symptoms, subjective complaints or objective changes in their well-being to the Investigator or the site personnel, regardless of the perceived relationship between the event and the trial vaccine.

The Investigator will assess the relationship between trial vaccine and each occurrence of AE/SAE.

SAEs and AEs leading to vaccine withdrawal or trial discontinuation will be collected throughout the trial.

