12.7.1.1 Analysis of Unsolicited AEs and Solicited AEs

An overall summary of unsolicited AEs will be prepared for AEs occurring within 28 days after each dose, within 28 days after any dose, and all reported AEs (including those reported at more than 28 days after any dose).

- Unsolicited AEs
- Related unsolicited AEs
- SAEs (includes solicited AEs)
- Related SAEs (includes solicited AEs)
- Grade 3 (severe) unsolicited AEs
- Grade 3 (severe) related unsolicited AEs
- Intercurrent medical conditions affecting immune response (includes solicited AEs)
- Medically attended AEs (includes solicited AEs)
- Related medically attended AEs (includes solicited AEs)
- AESIs (includes solicited AEs)
- Related AESIs (includes solicited AEs)
- Medically attended AEs (includes solicited AEs)
- Related medically attended AEs (includes solicited AEs)
- AESIs (includes solicited AEs)
- Related AESIs (includes solicited AEs)
- AEs leading to vaccine withdrawal
- AEs leading to withdrawal from trial

The overall summary will also be presented for overall and by sex (female/male)* and for any dose (dose 1 and dose 2) and include AEs for the duration of the trial.

The following summaries of unsolicited AEs by SOC and PT will further be provided, separately for AEs occurring within the first 28 days after each vaccination, within the 28 days after any vaccination, and all reported AEs (including those reported at more than 28 days after any dose) if not otherwise stated:

- Occurrence of unsolicited AEs
- Occurrence of related unsolicited AEs*
- Occurrence of SAEs (includes solicited AEs)*
- Occurrence of related SAEs (includes solicited AEs) *
- Occurrence of unsolicited AEs by maximum severity (mild / moderate / severe)*
- Occurrence of related unsolicited AEs by maximum severity (mild / moderate / severe) *
- Occurrence of SAEs by maximum severity (mild / moderate / severe) (includes solicited AEs)*

- Occurrence of related SAEs by maximum severity (mild / moderate / severe) (includes solicited AEs)*
- Occurrence of AESIs (includes solicited AEs)
- Occurrence of related AESIs (includes solicited AEs)*
- Occurrence of intercurrent medical conditions affecting immune response (includes solicited AEs)*
- Occurrence of medically attended AEs (includes solicited AEs)*
- Occurrence of related medically attended AEs (includes solicited AEs)*
- Occurrence of AEs leading to withdrawal from trial (includes solicited AEs)

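### SAP 10.7.1 defines treatment-emergent AEs by first occurrence or worsening, but its start-date rule also makes an AE that merely eases after a dose count as new

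*SAP*

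**What the plan says.** SAP 10.7.1 reaches its classification in three steps.

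- Definition: "A TEAE is any AE that first occurs or increases in severity or relationship to trial vaccine after the first dose of vaccine".
- Recording rule: "AEs which change in severity or relationship to trial vaccine are assigned a new start date and captured as a new record in the CRF".
- Conclusion: "Hence, an AE is defined as TEAEs if the start date/time is after the date/time of first vaccination".

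Solicited AEs are set apart: "All Solicited AEs are considered treatment emergent, even in the case that (partially) missing or conflicting date/time information is recorded or imputed".

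AEs with onset before Dose 1 are expected data, because SAP 10.7.3 states: "Diaries will also be used for collection of unsolicited AEs in the week before the first vaccination as well as on each vaccination day". For reporting, SAP 12.7.1.1 says: "An overall summary of unsolicited AEs will be prepared for AEs occurring within 28 days after each dose". It also has the tables by system organ class and preferred term produced "separately for AEs occurring within the first 28 days after each vaccination". SAP Appendix 4 lists these as Tables 14.3.2.16.1 to 14.3.2.16.3 and, by maximum severity, 14.3.2.20.1 to 14.3.2.20.3 (any dose, Dose 1, Dose 2). Unsolicited AEs in the 28-day windows are a primary safety endpoint (Protocol 4.2.1, SAP 9.4).

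**The concern.** The definition has a direction: only a first occurrence or an increase counts. The recording rule has none: any change opens a new record with a new start date. The conclusion then looks at the start date alone. It follows from the definition only if every change is an increase, and easing or a downgrade in relationship is also a change. Nothing elsewhere in the SAP or protocol limits the new start date to worsening, ties an eased record to its parent AE, or takes eased records out of the post-dose tables.

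This matters more than usual here because there is no control arm. Under Protocol 9.1.1 and SAP 10.7 subjects act as their own control, with the week before Dose 1 as the baseline. If a baseline complaint that is improving is relabelled as a post-dose event, the comparison the design relies on is distorted. The same mechanism can carry an AE from the Dose 1 period into the Dose 2 tables.

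**Working it through.** The documents give no rate or expected count for this point, so there is no plan figure to reproduce. The check is of the logic, followed by a scale.

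**1. Definition against working rule.** Let *g0* be the grade at onset and *g1* the grade after a change that falls after Dose 1, each from 1 to 3.

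- Definition: treatment-emergent if onset is after Dose 1, or *g1* > *g0*.
- Working rule: keep the onset record; if *g1* ≠ *g0*, add a record starting at the change; treatment-emergent if any record starts after Dose 1.

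Cases: 2 onsets × 3 × 3 grades = 18.

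| Onset | Grade after Dose 1 | Cases | Definition | Working rule | Records starting post-dose |
|---|---|---|---|---|---|
| Before Dose 1 | unchanged | 3 | no | no | 0 |
| Before Dose 1 | higher | 3 | yes | yes | 1 |
| Before Dose 1 | **lower** | 3 | **no** | **yes** | 1 |
| After Dose 1 | unchanged | 3 | yes | yes | 1 |
| After Dose 1 | higher | 3 | yes | yes | 2 |
| After Dose 1 | lower | 3 | yes | yes | 2 |

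The two disagree in 3 of 18 cases: onset before Dose 1, easing 2→1, 3→1 or 3→2. For AEs that begin after Dose 1 and ease, the classification is unaffected, but one AE yields two post-dose records.

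**2. Carry-over to Dose 2.** With doses on Days 1 and 29, the windows (dosing day plus 28 days) are Days 1–29 and Days 29–57. A moderate AE that starts on Day 20 and becomes mild on Day 31 has records starting on both days. The second falls in the Dose 2 window although nothing new happened after Dose 2. This assumes that windows are assigned by start date.

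**3. Relationship.** Protocol Appendix 9 allows two levels, related and unrelated, and lets the investigator revise the assessment on follow-up information. A revision from related to unrelated is a change, so the rule gives it a new start date. This bites mainly on the Dose 2 window, since an AE before any vaccine would not ordinarily have been assessed as related.

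**4. Scale.** SAP 6.3 gives 129 enrolled subjects. If all are in the safety set, each subject wrongly added is 100/129 = 0.78, or about 0.8 percentage points. As an illustration only, 1, 3 or 5 such subjects would be 0.8, 2.3 or 3.9 points. If the 129 were spread evenly over the seven co-morbidities (an assumption), a stratum would hold 129/7 = 18.4 subjects and one subject would be 100/18.4 = 5.4 points.

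**5. Check of the fix.** If a later record counts as new only when it exceeds the highest level before the dose, the mismatches in step 1 fall from 3 of 18 to 0 of 18. For AEs that begin after Dose 1 and ease, post-dose records fall from 2 to 1. The comparator matters. A pre-dose Grade 3 AE that eases to 1 and returns to 2 rises relative to its preceding record (2 > 1), but not relative to its highest pre-dose grade (2 < 3), so comparing with the preceding record alone would mislabel it.

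**The case against.** The case for leaving the text alone is that the definition shows the intent and that few AEs can be affected. Much of this stands.

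- **Exposure is narrow.** Protocol 6.4 delays vaccination for a Grade 2 or higher active infection or other acute disease close to dosing. A Grade 1 AE cannot ease to a lower grade, because Grade 0 means no AE. Pre-existing conditions go to medical history (Protocol 9.1.5), and expected fluctuation that does not worsen is not an AE (Protocol Appendix 9). What remains is mainly AEs arising between consent and Dose 1 that are Grade 2 or higher without triggering the delay rule, some AEs still running at Dose 2, and relationship revisions, which the grade limits do not touch.
- **Counting by subject absorbs most duplicates.** An AE that began after Dose 1 and eases adds nobody to the any-dose tables, and maximum-severity tables absorb the lower-grade record within the same window.
- **No output listed in Appendix 4 names treatment-emergent AEs.** The effect on reported tables therefore runs through the new start date. The SAP gives no explicit algorithm for assigning AEs to windows; use of the start date is the natural reading, not a stated rule.
- Solicited AEs keep their status in any case, and all analyses are descriptive.

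These points limit the size. None of them removes the contradiction in SAP 10.7.1.

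Two stronger readings are tempting and not supported. A reader might infer from Protocol Appendix 9, "New or updated information will be recorded in the originally completed eCRF", that sites may not open a new record, so that real worsening keeps its pre-dose date and is missed. That sentence concerns follow-up information and is compatible with adding a record inside the same eCRF; the eCRF itself is not among the documents. A reader might also infer that a sizeable share of subjects will have false post-dose events. The documents contain no rate of ongoing AEs or of easing on which to base such a figure.

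**Conclusion.** SAP 10.7.1 is wrong as written. Its working rule gives a result that its own definition excludes whenever an unsolicited AE with onset before Dose 1 eases afterwards. The same new start date can place an AE that began after Dose 1 and eases after Dose 2 in the Dose 2 tables. Both bear on a primary safety endpoint in a trial without a control group.

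The number of subjects affected cannot be derived from the documents and is probably small. Each one adds about 0.8 percentage points overall, assuming that all 129 are in the safety set and that the subject would not otherwise be counted in that row. The effect on the tables also assumes that windows are assigned by start date. The logical fault in 10.7.1 depends on neither assumption.

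**What to change.** In SAP 10.7.1 and 12.7.1.1:

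1. Link successive records of the same AE, for example by the same term with the end date of one record adjoining the start date of the next.
2. Treat a later record as new after a dose only if its severity or relationship exceeds the highest level recorded for that AE before that dose.
3. Otherwise keep the onset date of the first linked record, both for treatment-emergent status and for assignment to the 28-day windows. State that windows are assigned on this date.

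No change to the eCRF or to Protocol Appendix 9 is needed. At most, confirm that sites did open a new record when an AE worsened, since the start-date rule relies on it.

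The cost is a few sentences of SAP text and a short linking step in the AE derivation, made before database lock. No new data are required.
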